STUDY PROTOCOL PLAN AND STATISTICAL ANALYSIS PLAN (SAP)

UNIVERSITY CEU CARDENAL HERRERA

Principal investigator: [name] [name]

TITLE: Ultrasound Probe Pressure on the Intratendon Doppler Signal in Patellar Tendinopathy

Research and Ethics Committee of CEU Cardenal Herrera University Number: CEI20/073

NCT ID:

DATE: 12-09-2020

STUDY PROTOCOL PLAN

Objectives:

The objectives of our study have been the following:

- Analyze the influence of the pressure exerted on the probe on the variables of area, number of signals, pixel intensity, perimeter, solidity, perfusion index, circularity, major and minor diameter of the intratendon Doppler signal in the evaluation of patellar tendinopathy.
- To study the relationship between the pressure exerted on the probe and intratendon perfusion in the Doppler evaluation of patellar tendinopathy.

Volunteers who want to participate in the study will read the general information of the study and sign the informed consent to participate in the study.

Once the informed consent has been read and delivered, the evaluator will check that they meet the inclusion criteria.

A quasi-experimental study of a single group will be carried out, consisting of subjects with patellar tendinopathy with intratendon hyper vascularization. Intratendon vascularization will be quantified using a proprietary methodology using ImageJ 1.47v image analysis software, determining the different variables related to the Doppler signal within an intratendon region of interest.

The first contact with the patient likely to participate in the project will always be made by the same researcher who will duly inform them of the study and provide informed consent in case of accepting participation for the performance of the exploratory ultrasound. Subsequently, a general questionnaire will be completed, where sociodemographic data and other data referring to the injury and sports practice are collected, also adding the VISA-P questionnaire that assesses the symptomatic severity, the severity of the symptoms and the capacity functional function in patients with patellar tendinopathy. Lastly, the ultrasound examination will be carried out in power-Doppler mode.

The ultrasound examination will begin with the positioning of the patient on the table in

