the supine position and with both knees extended. At the level of the knee to be explored, a support with an articulated arm will be placed where the probe attached to the force meter will be fixed. After positioning the articulated arm, a power-Doppler ultrasound scan of the intratendon vascularization will be carried out, making longitudinal cuts of the patellar tendon and using previously pre-established Doppler optimization parameters for all patients. The optimization parameters of the power-Doppler signal will be set at a Doppler frequency of 6.7 MHz, pulse repetition frequency (PRF) of 0.7 kHz. The lowest wall filter and a standardized gain just below the level that produces random noise will be applied.

This examination will be repeated several times with different probe pressures, which will be quantitatively adjusted through the force sensor and maintained with the articulated arm. A 4-second static video will be recorded of the longitudinal section that presents a higher Doppler signal in each of the scans at different probe pressures.

These videos will be saved for later analysis with ImageJ 1.47v software (Wayne Rasband, National Institutes of Health, USA, 2012) to determine and quantify the presence of intratendon Doppler signal.

The processing and analysis of the videos and images will be carried out on the image with the highest and lowest Doppler signal of each stored video. Once the image has been scaled, a region of interest (ROI) with dimensions capable of encompassing the intratendon Doppler signal will be selected individually.

To quantify the Doppler signal, the saved image with the highest Doppler signal of each video was selected and the area of color pixels was calculated.

To quantify the flux, the pixel color mean of the Doppler signals of each image was calculated. The mean pixel color of the image with the highest signal was considered as data of the maximum systolic velocity, and the one with the lowest signal as the final diastolic velocity. These data were transferred to the IR formula, obtaining a value associated with the intratendinous flow pattern (perfusion index).

In the images that did not detect a Doppler signal, or did not present an intratendon Doppler signal in diastole, the IR was determined as 1, which represents normality in the musculoskeletal tissue.

In addition, the parameters of number of signals, mean intensity of the pixel, area,

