A univariate analysis of outliers will be carried out and their influence will be verified through the Z scores. Multivariate analysis of atypical cases and their influence will be carried out using the Mahalanobis distance.

Unusual cases will be removed from the analysis only if it is certain that they are wrong.

It will be checked whether the quantitative variables of interest follow a normal distribution (Kolmogorov-Smirnov test). The normality tests will be accompanied by the Q-Q normality graphs with and without trend that will aid interpretation and decision-making. In the event that any of the variables of interest does not conform to a normal distribution, a transformation of this will be carried out until it is achieved as long as its interpretation is not compromised.

Analysis of data

In the case of fulfilling the assumption of normality, parametric tests will be chosen and if not, the non-parametric alternatives will be chosen.

The measurement pattern used will be randomized, all subjects will be assigned to a minimum or a maximum probe pressure as the start of the measurements. The randomization factor (pressure) is included as a fixed effect, which will prevent a possible

interaction between pressure and the quantification of the Doppler signal.

To perform the statistical analysis, in the case that the variables present normality, the Pearson correlation coefficient will be used for quantitative variables. In order to better visualize the joint behaviour of both variables, scatter diagrams will be added and to determine the effect size and interpret the degree of shared variance, the coefficient of determination will be calculated. In the event that any variable does not present normality, the Spearman Rho correlation test will be chosen.

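### Each subject is scanned at several probe pressures, but the only inferential method named is a Pearson or Spearman correlation, with no pair, subject term or unit of analysis

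*Combined protocol and SAP*

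**What the plan says.** The second objective in the Study Protocol Plan is: "To study the relationship between the pressure exerted on the probe and intratendon perfusion". The first is the influence of pressure on nine Doppler variables, from area to minor diameter. On the examination, the protocol says: "This examination will be repeated several times with different probe pressures". It describes how each pressure is set and held: "which will be quantitatively adjusted through the force sensor and maintained with the articulated arm". One video is recorded per pressure. Neither the number of pressures nor their levels are listed.

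Under Analysis of data, the SAP contains four relevant statements:

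- A general rule: "parametric tests will be chosen and if not, the non-parametric alternatives will be chosen". No test is named.
- On order: "all subjects will be assigned to a minimum or a maximum probe pressure as the start of the measurements", followed by "The randomization factor (pressure) is included as a fixed effect". No model is named.
- The method: "in the case that the variables present normality, the Pearson correlation coefficient will be used for quantitative variables", with Spearman's rho if normality fails.
- The effect size: "to determine the effect size and interpret the degree of shared variance, the coefficient of determination will be calculated".

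No paired, repeated-measures, random-effect or subject term appears anywhere in the document.

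**The concern.** A correlation test treats its data points as independent. Here the natural data point is a scan, because pressure changes from scan to scan, and scans of one tendon are not independent. The SAP neither rules out pooling all scans nor offers a named alternative.

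The other statements do not fill the gap. The general rule names no test for the first objective. A correlation coefficient has no fixed effects, so the fixed-effect sentence needs a model that is not given. Its meaning is also unclear: what is randomised is the starting pressure, which suggests starting order, but the text in brackets says pressure.

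Two things are at stake. The first is the validity of the p-value. The second is the effect size. Pooled R² is a share of total variance, including differences between people, whereas the question is how the signal within a tendon responds to pressure. No effect per unit of pressure is planned.

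**Working it through.** The plan states no figure to reproduce: there is no sample size, number of pressures, alpha, effect size or SD. Everything below is therefore assumed: 20 subjects, 5 equally spaced pressures, non-pressure variance 1 (between subjects ICC, within subject 1 - ICC), two-sided 5%. Simulated figures use 10,000 replicates per setting, or 6,000 for varying slopes.

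**1. No effect, equal slopes: size of the pooled test.** Let τ be the between-subject SD of actual pressure in steps, and k = 5. The within-subject variance of the pressures is s² = (4+1+0+1+4)/4 = 2.5, so s²/k = 0.5. The intraclass correlation of pressure is

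ρ = (τ² - 0.5) / (τ² - 0.5 + 2.5).

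The true variance of the pooled statistic, relative to what the test assumes, is about V = 1 + (k-1)·ρ·ICC. The rejection rate is about 2[1 - Φ(1.96/√V)].

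| τ (steps) | ρ | V at ICC 0.3 / 0.5 / 0.8 | Formula, % | Simulated, % |
|---|---|---|---|---|
| 0 (common pressures) | -0.25 | 0.70 / 0.50 / 0.20 | 1.9 / 0.6 / 0.0 | 2 / <1 / 0 |
| 0.5 | -0.111 | 0.87 / 0.78 / 0.64 | 3.5 / 2.6 / 1.5 | 3.5 / 2.9 / 1.2 |
| 1 | 0.167 | 1.20 / 1.33 / 1.53 | 7.4 / 9.0 / 11.3 | 7.2 / 8.5 / 10.7 |
| 2 | 0.583 | 1.70 / 2.17 / 2.87 | 13.3 / 18.3 / 24.7 | 12.7 / 18.2 / 25.2 |

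The error changes sign where τ² = 0.5, at about 0.71 of a step. Pooled Spearman behaves similarly (12.0 / 16.8 / 23.6% at τ = 2).

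**2. No mean effect, common pressures, slopes varying between subjects (SD 0.2 per step).** With Sxx the sum of squared pressure steps in one subject, the true variance of a slope is 0.04 + (1-ICC)/Sxx. Pooling assumes (1 + 0.04·Sxx/k)/Sxx.

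- 5 pressures (Sxx = 10), ICC 0.3: 0.110/0.108 = 1.02. Formula 5.2%, simulated 5.0%.
- 10 pressures (Sxx = 82.5), ICC 0.3: 0.0485/0.0161 = 3.0. Formula 25.8%, simulated 26.1%.
- At ICC 0.8, simulated: 1.5% with 5 pressures and 23.1% with 10.
- With 3 pressures, simulated: 2.4% at ICC 0.3 and 0.1% at ICC 0.8.

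**3. Power, common pressures, equal slopes.** For a slope of -0.10 SD per step at ICC 0.8, the mean per-subject slope has standard error √(0.2/(10×20)) = 0.032, so the effect is about 3.2 standard errors. Pooling uses about √(1/200) = 0.071, so the same effect looks like 1.4 standard errors.

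| Slope per step | Pooled, % (ICC 0.1 / 0.3 / 0.5 / 0.8) | Per-subject slopes, % |
|---|---|---|
| -0.10 | 28 / 26 / 23 / 16 | 30 / 36 / 47 / 86 |
| -0.20 | 81 / 84 / 88 / 96 | 80 / 89 / 97 / 100 |
| -0.30 | at least 99 | at least 99 |

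The one-sample t-test on per-subject slopes rejected 4.4-5.7% in every no-effect setting.

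**4. R² at slope -0.30.** Pressure contributes 0.09 × 2 = 0.18 to the variance. Pooled: 0.18/1.18 = 0.15 (simulated 0.16-0.17). Within subject: 0.18/(0.18 + 0.8(1-ICC)) = 0.20 / 0.24 / 0.31 / 0.53 at ICC 0.1 / 0.3 / 0.5 / 0.8 (simulated 0.21 / 0.25 / 0.32 / 0.53). Pooled R² hardly moves while the within-tendon relationship ranges widely.

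**5. If the pair were two Doppler variables.** The SAP's wording does not exclude this. Then V = 1 + (k-1)·ICC². With 3 to 8 pressures and ICC 0.5 or 0.8, two unrelated variables correlate significantly in 11-40% of trials by formula and 10-43% simulated.

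**The case against.** The strongest reply is that this is under-specification, not a wrong analysis. Nowhere does the plan say that scans will be pooled, the fixed-effect sentence implies some model, and the objectives point to pressure against each Doppler variable as the pair. It is true that pooling is not stated and that the objectives suggest the pair. They do not give the unit of analysis, however, and a subject term is still absent.

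The inflation also depends on unsupported settings. It needs pressures that differ between subjects by more than about 0.7 of a step, or many pressures with varying slopes. A force sensor, an articulated arm and standardised procedures suggest controlled pressures. With common pressures and similar slopes the pooled test is conservative, and for large effects or ICC 0.1 it loses little. All of this stands, and it limits the size of the problem. It does not make the named method suitable: in the well-controlled case the cost is lost power and a diluted R².

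R² is a legitimate description of shared variance; the objection here is to its being the only effect size. Finally, a random-slope model may fail to converge: 11% of 300 no-effect fits did so (20 × 5, ICC 0.3, no true slope variation). That is a reason to name a fallback in advance. Taking the per-subject slope test as primary would also be valid.

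**Conclusion.** The concern holds, and the analysis needs correcting before it is run. The design gives repeated measurements within subject, while the only named method ignores the subject. On the pooled reading, and with the assumed inputs, the test ranges from almost never rejecting a true null to rejecting it about 25% of the time, and power for a small effect can fall from 86% to 16%. Which applies depends on facts the plan omits: the pressure levels, their number, the sample size and the correlation within subject. For strong effects with common pressures, the significance result would barely change, but R² would still understate how closely the signal in a tendon follows pressure.

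**What to change.** In Analysis of data:

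1. State the pair (probe pressure against each Doppler variable) and that the subject is the unit of inference.
2. Name one primary analysis: a mixed model with pressure and randomised starting order as fixed effects, a random subject intercept and a random pressure slope.
3. If the random slope cannot be estimated, use a one-sample test of per-subject slopes, not a random intercept alone. With slope SD 0.2 per step and no mean effect, the intercept-only model rejects 9-16% at 5 pressures and 32-44% at 10.
4. For non-normal outcomes, and for the perfusion index (which the protocol sets to 1 when no signal, or no diastolic signal, is seen), test the per-subject Spearman coefficients, counting a subject whose readings are all equal as 0. This rejected 4.5-6.0% across the no-effect settings (5.0-5.4% with capped values).
5. Report the slope per unit of pressure with a 95% CI. Keep R² and the scatter plots as description, with points joined within subject.
6. Reword the fixed-effect sentence to say that it means starting order, once the authors confirm this. Pressure has its own term in the model.

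The cost is SAP wording and slightly more analysis work on the same data. The one drawback is that the random slope may not be estimable with few subjects or pressures, which item 3 covers.

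### The SAP's only named effect size, R², mixes the tendon's response with the pressure levels chosen and the spread in the data, so it does not say how much the Doppler signal changes

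*Combined protocol and SAP*

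**What the plan says.** The ultrasound section of the study protocol plan describes a scan that is "repeated several times with different probe pressures, which will be quantitatively adjusted through the force sensor and maintained with the articulated arm". Under Analysis of data, the SAP adds that "all subjects will be assigned to a minimum or a maximum probe pressure as the start of the measurements", and that "The randomization factor (pressure) is included as a fixed effect". Pressure is therefore a factor that the investigator sets, with several levels per subject. The documents give no pressure values, number of levels or spacing.

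For the analysis itself, "in the case that the variables present normality, the Pearson correlation coefficient will be used for quantitative variables". Within that branch, "to determine the effect size and interpret the degree of shared variance, the coefficient of determination will be calculated". For the other branch, "In the event that any variable does not present normality, the Spearman Rho correlation test will be chosen", with no effect size named.

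The SAP does not say which two variables are correlated. The second objective concerns the relation between probe pressure and intratendon perfusion, so I take the pair to be pressure and a Doppler variable. That is an inference.

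No slope, change per unit of force or contrast between pressure levels is planned. The Exploratory Data Analysis section promises means, SDs, medians, interquartile ranges and confidence intervals, but does not say that these will be given by pressure level, and they are not differences.

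**The concern.** Shared variance is a natural description when both variables vary freely in a sampled population. Here the variance of pressure is a design choice. Two groups with identical tendons and equipment could report quite different values of R² only because one used a wider or differently spaced set of pressures.

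The first objective is to analyse how pressure influences a list of Doppler variables. A reader of the results will want to know how much area, or how many signals, are lost between light and firm contact. R² does not give that. Because the plan does not state the levels, a reader also could not judge what range lies behind a reported R².

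The repeated scans add a second problem. If all scans from all subjects go into one correlation, differences between subjects in baseline vascularity enter the denominator and lower R², even when every tendon responds in the same way.

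**Working it through.** The documents give no expected correlation, slope, SD, sample size or pressure level, so there is no figure of the plan's own to reproduce. All numerical inputs below are assumptions in arbitrary units.

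**1. Dependence on the pressure levels (linear response).** With slope b, variance of the set pressures V and residual SD s,

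R² = b²V / (b²V + s²).

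Write o = R²/(1 − R²) = b²V/s². Doubling the range multiplies V by 4 and halving it divides V by 4. Five equally spaced levels on [−1, 1] have V = (1 + 0.25 + 0 + 0.25 + 1)/5 = 0.5. The two end levels alone have V = 1, which is a factor of 2. If V changes by a factor c, the new R² is c·o/(1 + c·o).

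| Starting R² (assumed) | o | Range doubled (c = 4) | Range halved (c = 1/4) | End levels only, instead of five (c = 2) |
|---|---|---|---|---|
| 0.20 | 0.25 | 1/2 = 0.50 | 0.0625/1.0625 = 0.06 | 0.5/1.5 = 0.33 |
| 0.40 | 0.667 | 2.667/3.667 = 0.73 | 0.167/1.167 = 0.14 | 1.333/2.333 = 0.57 |

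A simulation agrees (20 subjects, 5 levels, true slope −1, residual SD 1, 2000 runs). For pressure ranges of 1, 2 and 4 units, mean R² was 0.12, 0.34 and 0.67, while the mean estimated slope was −0.99, −1.00 and −1.00.

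**2. Dependence on the response.** With the range fixed at 2 units, five levels (V = 0.5) and s = 1, slopes of 0, 0.25, 0.5, 1 and 2 give R² of 0.00, 0.03, 0.11, 0.33 and 0.67. R² does carry information on the response when the levels are held fixed.

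**3. Dependence on between-subject spread.** If scans are pooled and subjects differ in baseline with SD t, pooled R² = b²V/(b²V + s² + t²). With b = 1, V = 0.5 and s = 0.5 this is 0.5/(0.75 + t²). For t = 0, 0.5, 1 and 2 it gives 0.67, 0.50, 0.29 and 0.11. The within-subject R² stays at 0.5/0.75 = 0.67 throughout.

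**4. Does a slope avoid the problem?** Only if the response is close to linear. With five equally spaced levels starting at zero and noise SD 0.2:

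- Exponential decay, y = exp(−x): widening the range from 2 to 4 moves the fitted slope from −0.42 to −0.23, and R² from 0.65 to 0.60.
- Linear fall from 1 to a floor of zero reached at x = 1: widening the range from 1 to 2 moves the slope from −1.0 to −0.5, and R² from 0.76 to 0.63.

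In both cases the slope depends on the range more than R² does, and a wider range lowers R². A difference between two named levels has no such dependence, because it refers to those levels only.

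**The case against.** The strongest reply is that R² is not empty here. It is zero when the slope is zero, whatever the range, and it rises with the slope at a fixed range (step 2). If every subject is scanned at the same levels, as the minimum-or-maximum start suggests, R² can rank the Doppler variables by how much of their variation pressure accounts for. A reader might infer that R² reflects only the chosen range and says nothing about the tendon's response. The formula and step 2 rule that out.

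A second reply is that the obvious substitute, change per unit of force, has the same weakness if the response is curved or reaches a floor. The protocol itself provides for images with no Doppler signal and then assigns a perfusion index of 1, so a floor is plausible. This stands, and step 4 shows it. It counts against a slope as the default, but not against differences between stated levels.

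It is also true that the plan specifies no regression that would already supply an estimate, that R² is attached only to the Pearson branch, and that the first objective does not explicitly ask for a per-unit figure. These points narrow the concern and raise the cost of the fix a little. They leave the plan without any stated measure of how much a Doppler variable changes.

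**Conclusion.** The concern holds in a limited form. In the Pearson branch the only effect size is R², read as shared variance, although pressure is set by the investigator and repeated within subjects. R² mixes response, chosen levels, residual spread and, if scans are pooled, between-subject spread. It can describe and rank within this study, but it cannot state the amount of change or be carried to a study with other levels.

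The possible distortion is large. Under a linear response, R² moves from 0.20 to anywhere between 0.06 and 0.50 as the range is halved or doubled; under pooling, it moves from 0.67 to 0.11 as the between-subject SD goes from 0 to 2. These sizes rest on assumed starting values, and the range figures rest on linearity; with a curved response the direction can reverse. The conclusion also assumes that pressure is one of the two correlated variables.

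This is a matter of interpretation and reporting. Nothing in the documents shows a figure to be wrong or the data collection to be unfit. I would class it as a cheap improvement.

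**What to change.** Replace the sentence on the coefficient of determination with the following content:

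- State the force levels used, with their unit, and which variables enter each analysis.
- Define the effect size for each Doppler variable as the within-subject difference between those force levels, in the variable's own units with a 95% CI. Obtain it from a repeated-measures model or a paired analysis, so that the interval does not treat scans from one subject as independent.
- Report change per unit of force only where the relation is shown to be approximately linear.
- Keep R², if wanted, as description, and do not read it as shared variance or as strength of effect.

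Defining the effect size this way also covers the Spearman branch, which has none at present. The cost is one additional repeated-measures analysis per variable and a short SAP paragraph. No extra scans or participants are needed.
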